# Study Summary

Title: Measuring Physical Activity in Transfusion Dependent Patients

with Myelodysplastic Syndrome (MDS)

**Précis:** This will be a single-arm, prospective, observational study that

will collect data on daily step count, heart rate, and anemiarelated symptoms in patients with red blood cell transfusion
dependent MDS. Patients will be provided with a wearable
activity monitor, which will be used to monitor daily step
count and heart rate. Devices will be paired with a centralized
data aggregation platform which will automatically collect and
store data. Anemia-related symptom and quality of life data will
be assessed using the FACT-An questionnaire at baseline
and then twice a week during the study period. Feasibility will
be measured by accrual rate, Fitbit compliance rate and study
completion rate. Acceptability will be measured by a
satisfaction survey and a brief interview at the end of 3-month

study.

**Objectives:** Primary:

• To assess the feasibility and patient acceptability of using a Fitbit to monitor daily step count and heart rate.

Secondary:

• To graph changes in daily step count, average daily resting heart rate, Fact-An score (assessed before and one day after each transfusion), and hemoglobin level.

Patients will be given an activity tracker to wear continuously

**Population:** Red blood cell transfusion dependent patients with MDS

Phase: Pilot Study

Number of Sites: 1 site (TJUH)

,

**Intervention:** for 90 days

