# Twice a week

Complete FACT-An questionnaire. Assess adherence with device.

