# 1.4.2 Secondary

 To graph changes in daily step count, average daily resting heart rate, Fact-An score (assessed twice a week), and hemoglobin level.

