# 2 Study Design

This is a single arm, prospective, observational pilot study that will collecting data on daily step count, heart rate, and anemia related symptoms. The study population will include RBC transfusion dependent MDS patients who are ambulatory and in the outpatient setting. Patients will be given a wearable activity monitor and instructed to wear it continuously for 90 days. Baseline FACT-An questionnaire will be obtained to assess anemia related symptom data. Patients will have their CBC checked two times weekly and a FACT-An questionnaire will be administered twice a week (either on paper or electronically, based on patient preference). Activity data will be automatically collected from the Fitbit and stored using a centralized data aggregation platform. We will aim to collect data on 21 patients, with an estimated enrollment period of 9 months.

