#### 9 Statistical Considerations

#### 9.1 **Analysis Plans**

**Primary Analysis:** The first aim of this study is to assess the feasibility of activity monitoring. This will be defined as usage of the Fitbit device for at least 80% of the 90 days under observation. The overall study period compliance rate along with a one-sided exact 95% confidence interval will be estimated. The device will be considered to have acceptable feasibility if the lower bound of the CI is above 0.6 or, equivalently, if at least 17/21 (81%) of participants are compliant for at least 70% of the days under observation.

Accrual rate and retention rate for the study will also be calculated.

Quantitatively, participants will complete the Client Satisfaction Quesionnaire-8 item version (CSQ-8), a validated measure that elicits the client's perspective on the value of services received. Qualitatively, we will interview each participant at the end of their 90-day participation to understand their perceived barriers and facilitators of using Fitbit in their daily activities and elicit their feedback to refine future study design. Interviews will be digitally audio-recorded and transcribed verbatim. Transcripts will be analyzed with a pre-defined code book to summarize participant's experience and comments.

**Exploratory Analyses:** Descriptive statistics will be used to outline patient characteristics and report Fact-An results. We will plot daily step count, average daily resting heart rate, hemoglobin levels, and Fact-An scores. We will use multivariate analyses to identify relationships between these variables and to determine if pretransfusion step count and/or heart rate predict post-transfusion FACT-An results.

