# Please circle or mark one number per line to indicate your response as it applies to the past 7 days.

	EMOTIONAL WELL-BEING	Not at all	A little bit	Som e-	Quite a bit	Very much
GE1	I feel sad	0	1	what 2	3	4
GE2	I am satisfied with how I am coping with my illness	0	1	2	3	4
GE3	I am losing hope in the fight against my illness	0	1	2	3	4
GE4	I feel nervous	0	1	2	3	4
GE5	I worry about dying	0	1	2	3	4
GE6	I worry that my condition will get worse	0	1	2	3	4

	FUNCTIONAL WELL-BEING	Not at all	A little bit	Som e- what	Quite a bit	Very much
GF1	I am able to work (include work at home)	0	1	2	3	4
GF2	My work (include work at home) is fulfilling	0	1	2	3	4
GF3	I am able to enjoy life	0	1	2	3	4
GF4	I have accepted my illness	0	1	2	3	4
GF5	I am sleeping well	0	1	2	3	4
GF6	I am enjoying the things I usually do for fun	0	1	2	3	4
GF7	I am content with the quality of my life right now	0	1	2	3	4

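### The exploratory prediction question in 9.1 fixes neither the predictor days nor the FACT-An score used; with a 7-day recall, shared days can look like prediction (minor)

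*Combined protocol and SAP*

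**What the plan says.** Under Exploratory Analyses, section 9.1 states the method in one clause, "We will use multivariate analyses to identify relationships between these variables", and the question in the next, "to determine if pretransfusion step count and/or heart rate predict post-transfusion FACT-An results". It gives no predictor window, index score, lag, prior-score term or handling of repeated transfusions within a patient. No other section supplies a predictor window or a model.

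The FACT-An form in Appendix B asks for "your response as it applies to the past 7 days".

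The protocol gives two schedules for FACT-An. The secondary objective in the Study Summary reads "Fact-An score (assessed before and one day after each transfusion". The précis in the same summary says baseline "and then twice a week during the study period". Twice-weekly timing also appears in the Schematic of Study Design ("Complete FACT-An questionnaire. Assess adherence with device", under its twice-weekly box), 1.4.2 ("Fact-An score (assessed twice a week"), 1.5.2, section 2 ("a FACT-An questionnaire will be administered twice a week"), 5.3, 6.1 and Appendix A.

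Section 13.3 lists the transfusion date among the data collected, together with FACT-An, daily step count and resting heart rate.

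**The concern.** A questionnaire completed after a transfusion is not necessarily a report on the time after it. With a 7-day recall, an early post-transfusion FACT-An mostly describes the days before the transfusion, which are the days from which the steps and heart rate are drawn. If patients walk more on days when they feel better, predictor and outcome correlate because they describe the same days, even if pre-transfusion activity carries no information about how the patient feels afterwards.

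Section 1.2 gives the long-term aim as a more personalized approach to transfusion that uses tracker data. A correlation produced by shared days could be carried into that work as evidence that the tracker predicts response. The exploratory label does not warn the reader, because it does not show how many days are shared.

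**Working it through.** **Plan's own figure.** The documents give no figure for this analysis. The only sizing figure is for compliance (9.2): with 21 patients and success at 17 or more, the exact binomial test has size 0.037 at a true rate of 60% and power 0.80 at 85%. The stated 80% reproduces, and nothing below bears on it.

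**Shared days by lag.** Let the transfusion be day 0 and the score be taken on day d. The recall covers days d−6 to d if the completion day counts, and d−7 to d−1 if not. Days before day 0 number 6−d or 7−d:

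| Score taken on day | Pre-transfusion recall days (of 7) |
|---|---|
| 1 | 5 or 6 |
| 2 | 4 or 5 |
| 3 | 3 or 4 |
| 4 | 2 or 3 |
| 5 | 1 or 2 |
| 6 | 0 or 1 |
| 7 or later | 0 |

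These counts need only the recall period.

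**Twice-weekly schedule.** Assume gaps of 3 and 4 days and a transfusion equally likely on any day of the week. The waits to the first score at least one day later are 3, 2, 1, 4, 3, 2 and 1 days, with mean 16/7 = 2.29. The mean pre-transfusion share is (6 − 16/7)/7 = 26/49 = 53% with the completion day counted, and (7 − 16/7)/7 = 33/49 = 67% without.

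**What overlap alone could produce (illustration).** The following are assumptions, not figures from the documents: independent days; daily wellness with variance 1; steps correlated r with same-day wellness; FACT-An equal to the mean of its recall days plus noise of SD s; no link from pre-transfusion activity to later wellness. With a predictor window of w days, k of them inside the recall period,

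correlation = [r·k/(7w)] / √[(1/w)(1/7 + s²)].

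For r = 0.5, w = 7, s = 0.2 and k = 6: (0.5 × 6/49)/√(0.1429 × 0.1829) = 0.0612/0.1616 = 0.38. Ranges below run over the two ways of counting the completion day.

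| r | w (days) | s | Day 1 | Day 4 |
|---|---|---|---|---|
| 0.5 | 7 | 0.2 | 0.32–0.38 | 0.13–0.19 |
| 0.5 | 7 | 0 | 0.36–0.43 | 0.14–0.21 |
| 0.5 | 7 | 0.4 | 0.25–0.29 | 0.10–0.15 |
| 0.5 | 3 | 0.2 | 0.29 | 0.19–0.29 |
| 0.3 | 7 | 0.2 | 0.19–0.23 | 0.08–0.11 |
| 0.1 | 7 | 0.2 | 0.06–0.08 | 0.03–0.04 |
| 0 | any | any | 0 | 0 |

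The fall from day 1 to day 4 depends on the window. With 3 days and the completion day not counted, all three predictor days lie inside the recall at both lags.

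A simulation on the same assumptions used 21 patients, 6 transfusions each at 15-day intervals, and a patient-centred regression at two-sided 5%. Share of runs with a significant slope for steps:
- r = 0.5, 7-day window, s = 0.2: 92–98% at day 1, 26–50% at day 4.
- The same with s from 0 to 0.4: 72–99.5% at day 1.
- r = 0.5, 3-day window, s = 0.2: about 85% at day 1, 52–86% at day 4.
- r = 0.1, 7-day window, s = 0.2: 10–12% at day 1, 6–7% at day 4.
- r = 0: about 5%.

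**Effect of adjustment** (r = 0.5, 7-day window, s = 0.2, day 1). A prior score taken 2 days before transfusion brings 92–98% down to 44–84%. One taken on the transfusion day brings it to 15–24%. Adjustment reduces the overlap effect but does not remove it.

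Only steps were worked through. Heart rate would follow the same rows at the same absolute r.

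**The case against.** The clause is peripheral. The secondary objective is to graph the measures, the prediction question appears once under an exploratory label, and no test, alpha level or decision depends on it. Leaving windows and lags open in a 21-patient pilot is common. This stands, and it keeps the point minor.

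A reader might infer that the plan has chosen a model that ignores the earlier score. The documents do not support that. Section 9.1 does not say whether it adjusts, and a multivariate analysis of variables that include FACT-An could do so. Nor is the protocol wholly silent on lag, since the Study Summary objective gives one day after transfusion. But that timing conflicts with the rest of the protocol and is the lag with most overlap among scores taken after the transfusion day.

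A reader might also take the rejection percentages as false-positive rates for this trial. They are not. Section 9.1 names no test, and r, the noise, the window and the independence of days are all assumed. The question as written also concerns the recorded score, and a day-1 score that mostly describes earlier days really is predictable from earlier steps. Overlap misleads only when the result is read as saying something about the patient's state after transfusion. That is the reading that would matter for the aim in 1.2.

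Finally, separating the windows does not settle the matter if symptoms persist from day to day. In the same simulation at a 7-day lag and r = 0.5, a day-to-day autocorrelation of 0.8 gives significance in 51–78% of runs, part of it genuine persistence. A non-overlap analysis is therefore a useful check but should not be the main analysis.

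**Conclusion.** The point holds as a minor, exploratory-level one. The shared-day counts follow from the 7-day recall alone: 5 to 6 of 7 days at day 1 and 2 to 3 at day 4. The average of 53% to 67% for the first twice-weekly score also assumes 3- and 4-day gaps and counts only scores at least one day after transfusion. Overlap can look like prediction only if activity and symptoms are linked on the same day. The size of the effect cannot be derived from the documents, so the correlations and rejection rates above are illustrations.

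It would be too strong to conclude that the planned analysis is invalid or that the trial's conclusions are at risk. The primary feasibility result and the sample size concern device compliance and are unaffected. The conflict between the two FACT-An schedules is a separate inconsistency that needs correcting whatever is decided about the analysis.

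**What to change.** 1. In 9.1, use the transfusion dates recorded under 13.3 to define the pre-transfusion window for steps and heart rate, and the index post-transfusion FACT-An by its lag.
2. Adjust for the last pre-transfusion FACT-An, account for repeated measures within patient, and report the number of shared recall days. State that adjustment reduces the overlap effect without removing it.
3. Describe results from overlapping scores as association, not prediction.
4. Optionally, add a sensitivity analysis restricted to scores with no shared days (lag of at least 6 days if the completion day counts, 7 if not). Report the cycles lost and say that day-to-day persistence can still carry association past that lag.
5. Separately, reconcile the FACT-An timing in the Study Summary objective with the twice-weekly timing in the précis, the schematic, 1.4.2, 1.5.2, section 2, 5.3, 6.1 and Appendix A.

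The cost is some wording in 9.1, one phrase in the Study Summary and a little more analysis. No new data are needed. The drawback of item 4 is that it under-represents frequently transfused patients. With regular intervals over 90 days and twice-weekly scores, a lag of at least 6 / at least 7 days keeps about 62% / 55% of post-transfusion scores at 15-day intervals, 43% / 32% at 10 days and 16% / 0% at 7 days. If only day-after scores are collected, none qualify, and items 2 and 3 are what remain.

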# 9.2 Sample Size Considerations

A sample size of 21 patients provides 80% power to reject the null hypotheses that the true compliance rate is less than or equal to 60% using a one-sided exact binomial tests of size 0.05 assuming the true rate is 85% or greater.

#### 10 Source Documents and Access to Source Data/Documents

Study staff will maintain appropriate medical and research records for this study, in compliance with ICH E6, and regulatory and institutional requirements for the protection of confidentiality of participant information. Study staff will permit authorized

representatives of SKCC and regulatory agencies to examine (and when required by applicable law, to copy) research records for the purposes of quality assurance reviews, audits, and evaluation of the study safety, progress and data validity.

# 11 Quality Control and Quality Assurance

Data obtained regarding activity level and compliance of study participants as measured by the wearable device stored in our central data aggregation platform will be correlated with hemoglobin level and FACT-An questionnaire results. Documents to be reviewed to obtain this data include clinic notes, FACT-An questionnaire results, CBC results, and activity logs from our central data platform on a weekly basis by members of investigational team. Data will be evaluated in compliance with our protocol. Quality assurance and quality control issues will be addressed by the principal investigator.

# 12 Ethics/Protection of Human Participants

#### 12.1 Ethical Standard

The investigator will ensure that this study is conducted in full conformity with the principles set forth in The Belmont Report: Ethical Principles and Guidelines for the Protection of Human Subjects of Research, as drafted by the US National Commission for the Protection of Human Subjects of Biomedical and Behavioral Research (April 18, 1979) and codified in 45 CFR Part 46 and/or the ICH E6.

#### 12.2 Institutional Review Board

The protocol, informed consent form(s), recruitment materials, and all participant materials will be submitted to the IRB for review and approval. Approval of both the protocol and the consent form must be obtained before any participant is enrolled. Any amendment to the protocol will require review and approval by the IRB before the changes are implemented in the study.

#### 12.3 Informed Consent Process

Informed consent is a process that is initiated prior to the individual agreeing to participate in the study and continues throughout study participation. Extensive discussion of risks and possible benefits of study participation will be provided to participants and their families, if applicable. A consent form describing in detail the study procedures and risks will be given to the participant. Consent forms will be IRB-approved, and the participant is required to read and review the document or have the document read to him or her. The investigator or designee will explain the research study to the participant and answer any questions that may arise. The participant will sign the informed consent document prior to any study-related assessments or procedures. Participants will be given the opportunity to discuss the study with their surrogates or think about it prior to agreeing to participate. They may withdraw consent at any time throughout the course of the study. A copy of the signed informed consent document will be given to participants for their records. The rights and welfare of the

participants will be protected by emphasizing to them that the quality of their clinical care will not be adversely affected if they decline to participate in this study. The consent process will be documented in the clinical or research record.

#### 12.4 Exclusion of Women, Minorities, and Children (Special Populations)

Individuals must be ≥ 18 years of age to participate in the study. Individuals of any gender or racial/ethnic group may participate.

# 12.5 Participant Confidentiality

Participant confidentiality is strictly held in trust by the investigators, study staff, and the sponsor(s) and their agents. This confidentiality is extended to cover testing of biological samples and genetic tests in addition to any study information relating to participants.

The study protocol, documentation, data, and all other information generated will be held in strict confidence. No information concerning the study or the data will be released to any unauthorized third party without prior written approval of the sponsor.

The study monitor or other authorized representatives of the sponsor may inspect all study documents and records required to be maintained by the investigator, including but not limited to, medical records (office, clinic, or hospital) for the study participants. The clinical study site will permit access to such records.

# 13 Data Handling and Record Keeping

The investigators are responsible for ensuring the accuracy, completeness, legibility, and timeliness of the data reported. All source documents must be completed in a neat, legible manner to ensure accurate interpretation of data. The investigators will maintain adequate case histories of study participants, and source documentation.

# 13.1 Data Management Responsibilities

Data collection and accurate documentation are the responsibility of the study staff under the supervision of the investigator. All source documents and laboratory reports must be reviewed by the study team and data entry staff, who will ensure that they are accurate and complete. Unanticipated problems and adverse events must be reviewed by the investigator or designee.

The study protocol, documentation, data, and all other information generated will be held in strict confidence. No information concerning the study or the data will be released to any unauthorized third party without prior written approval of the sponsor. Each participant will be assigned a unique identification number (ID) and this ID number will be the only identifying information on data form. A list linking ID numbers to names will be kept in a password-protected computer file accessible only to project staff.

# 13.2 Data Capture Methods

Data will be captured in multiple forms. Daily step count, compliance, and heart rate will be collected in an electronic format in a centralized data aggregation platform that is password protected. Data on hemoglobin and medical history will be collected from the electronic or paper medical record and transferred to an electronic database that is password protected. FACT-An questionnaire results will be obtained verbally via telephone and entered directly into the RedCap database. All data will be collected in an ongoing manner during the duration of the study.

#### 13.3 **Types of Data**

Types of data that will be collected include: laboratory (hemoglobin), transfusion date, number of units of blood transfused, outcome measure data (FACT-An questionnaire, daily step count, average daily resting heart rate, and compliance with wearable device). Reports to monitor enrollment will occur on an ongoing biweekly basis by the study team. Plans for data analysis and interim and final study reports will occur immediately after completion of data collection.

# 13.4 Study Records Retention

Study documents will be retained for a minimum of 2 years. These documents should be retained for a longer period, however, if required by local regulations.

#### 13.5 **Protocol Deviations**

A protocol deviation is any noncompliance with the clinical study protocol, Good Clinical Practice, or Manual of Procedures requirements. The noncompliance may be on the part of the participant, the investigator, or study staff. As a result of deviations, corrective actions are to be developed by the study staff and implemented promptly.

All deviations from the protocol must be addressed in study participant source documents and promptly reported to the IRB and other regulatory bodies according to their requirements.

# 14 Study Finances

#### 14.1 Funding Source

This study will be financed through the sponsorship of the Sidney Kimmel Cancer Center of TJUH.

#### 14.2 Conflict of Interest

Any investigator who has a conflict of interest with this study (patent ownership, royalties, or financial gain greater than the minimum allowable by their institution, etc.) must have the conflict reviewed by a properly constituted Conflict of Interest Committee with a Committee-sanctioned conflict management plan that has been reviewed and approved by the study sponsor prior to participation in this study. All Jefferson University Investigators will follow the TJU Conflicts of Interest Policy for Employees (107.03).

#### 14.3 Participant Stipends or Payments

Participants will be able to keep the Fitbit wearable device they used for the study after completion of observation. They will also receive \$40 via ClinCard as incentive for completing surveys.

# 15 Publication and Data Sharing Policy

This study will comply with the NIH Public Access Policy, which ensures that the public has access to the published results of NIH funded research. It requires scientists to submit final peer-reviewed journal manuscripts that arise from NIH funds to the digital archive PubMed Central upon acceptance for publication.

The International Committee of Medical Journal Editors (ICMJE) member journals have adopted a clinical trials registration policy as a condition for publication. The ICMJE defines a clinical trial as any research project that prospectively assigns human participants to intervention or concurrent comparison or control groups to study the cause-and-effect relationship between a medical intervention and a health outcome. Medical interventions include drugs, surgical procedures, devices, behavioral treatments, process-of-care changes, and the like. Health outcomes include any biomedical or health-related measures obtained in patients or participants, including pharmacokinetic measures and adverse events. The ICMJE policy requires that all clinical trials be registered in a public trials registry such as ClinicalTrials.gov, which is sponsored by the National Library of Medicine. Other biomedical journals are considering adopting similar policies. The ICMJE does not review specific studies to determine whether registration is necessary; instead, the committee recommends that researchers who have questions about the need to register err on the side of registration or consult the editorial office of the journal in which they wish to publish.

U.S. Public Law 110-85 (Food and Drug Administration Amendments Act of 2007 or FDAAA), Title VIII, Section 801 mandates that a "responsible party" (i.e., the sponsor or designated principal investigator) register and report results of certain "applicable clinical trials."

